### **Appendix 5.** Alcohol Use Disorders Identification Test

Each question has a set of responses with each response having a score ranging from 0 to 4. The summation of all response scores provides the total score. If after data query, inconsistent responses are still present for questions that should have been skipped based on responses to previous questions, the most conservative (higher) score or response will be selected for each individual question as well as summation of the total score.

Questions	0	1	2	3	4

1. How often do you have a drink containing alcohol?

(Skip to Questions 9 and 10 if Total Score for Question 1 = 0)

	Never	Monthly or less	2 to 4 times a month	2 to 3 times a week	4 or more times a week
2. How many drinks containing alcohol do you have on a typical day when you are drinking?	1 or 2	3 or 4	5 or 6	7, 8, or 9	10 or more
3. How often do you have six or more drinks on one occasion? (Skip to Questions 9 and 10 if Total Score for Questions 2 and 3 = 0)	Never	Less than monthly	Monthly	Weekly	Daily or almost daily
4. How often during the last year have you found that you were not able to stop drinking once you had started?	Never	Less than monthly	Monthly	Weekly	Daily or almost daily
5. How often during the last year have you failed to do what was normally expected from you because of drinking?	Never	Less than monthly	Monthly	Weekly	Daily or almost daily
6. How often during the last year have you needed a first drink in the morning to get yourself going after a heavy drinking session?	Never	Less than monthly	Monthly	Weekly	Daily or almost daily
7. How often during the last year have you had a feeling of guilt or remorse after drinking?	Never	Less than monthly	Monthly	Weekly	Daily or almost daily
8. How often during the last year have you been unable to remember what happened the night before because you had been drinking?	Never	Less than monthly	Monthly	Weekly	Daily or almost daily
9. Have you or someone else been injured as a result of your drinking?	No		Yes, but not in the last year		Yes, during the last year
10. Has a relative, friend, doctor, or another health worker been concerned about your drinking or suggested you cut down?	No		Yes, but not in the last year		Yes, during the last year

## Appendix 6. Efficacy Information from Truvada as PrEP in MSMs

			HIV Infections (Incidence per 100 PY)			Rate Difference
Clinical Trial	Sample Size Placebo (PY Follow-Up)	Sample Size Truvada (PY Follow-Up)	Placebo	Truvada	Rate Ratios in HIV Infection Rates, per 100 PY [95% CI]	in HIV Infection Rates, per 100 PY [95% CI]
PROUD	255 (222)	268 (243)	20 (9.0)	3 (1.2)	7.3 [2.2, 24.2]	7.8 [3.6, 12.0]
IPERGAY	201 (212)	199 (220)	14 (6.6)	2 (0.9)	7.3 [1.7, 31.6]	5.7 [2.0, 9.4]
iPrEX (URAI subgroup) at screening	753 (1054)	732 (1055)	56 (5.3)	23 (2.2)	2.4 [1.5, 3.9]	3.1 [1.5, 5.8]
Pool	1209 (1488)	1199 (1518)	90 {6.96}*	28 {1.44}*	5.1* [ 2.64 , 9.70] NI Margin: 1.62	5.5* [3.60, 7.47] NI Margin: 1.2

Source: PROUD from {McCormack 2015}; IPERGAY from {Molina 2015}; iPrEx from {Grant 2010}

Note: The NI margins are based on the lower 95% CI bounds (LCB); to preserve 50% of Truvada effect vs Placebo (square root of LCB) for the rate ratio, and to preserve 67% of Truvada effect vs Placebo (1/3 of LCB) for the rate difference.

\* The pooled incidence rate for placebo and F/TDF, based on equal weighting of three studies, are within {} which are used for estimating the rate ratio, and rate difference and their corresponding 95% CI.

# Appendix 7. TFV-DP Simulations to Support On-Treatment HIV Infections Analysis

Simulation analyses were conducted to define the period of time participants in DISCOVER are expected to have PBMC-associated TFV-DP concentrations associated with HIV prevention after cessation of study drug (F/TAF 200/25 mg or F/TDF 200/300 mg) to support an on-treatment efficacy sensitivity analysis.

Briefly, TAF and TDF are distinct prodrugs of the active intracellular metabolite, TFV-DP, which has a long half-life {Hawkins 2005}. The median PBMC-associated concentration of TFV-DP expected to be associated with HIV prevention following once daily administration of F/TDF for PrEP based on data from the iPrEX study was ~40 fmol/ $10^6$  cells {Anderson 2012b} As such, it is expected that PBMC-associated TFV-DP concentrations at or above this threshold will be associated with prevention of HIV-infection. Thus, the objective of this analysis was to define the period of time participants are expected to have TFV-DP concentrations  $\geq$  40 fmol/ $10^6$  cells after cessation of F/TAF or F/TDF taken once daily in DISCOVER. The methodology and results of these analyses are described below.

#### Methodology

#### **Studies Included in the Analysis**

For the simulations of TFV-DP from TAF, PBMC-associated TFV-DP PK data was included from a Phase 1 study in healthy volunteers (GS-US-380-4017). In this study, PBMC samples for TFV-DP were collected following administration of bictegravir/F/TAF 50/200/25 mg once daily for 28 days (N 26). Samples for TFV-DP were collected over a period of 28 days postdose after the last dose of study drug. Mean (CV%) trough concentrations of TFV-DP from this study (434.0 [108.7] fmol/10^6 cells) were similar to those observed with historical data following administration of F/TAF (200/25 mg with unboosted ARV agents or 200/10 mg with boosted ARV agents) in HIV-infected participants in the Phase 3 Study GS-US-311-1089 (430.2 [114.1] fmol/10^6 cells).

For the simulations of TFV-DP from TDF, PBMC-associated TFV-DP PK data was included from a Phase 1 study in HIV-infected patients {Hawkins 2005}. In this study, HIV-infected participants who were on stable TDF 300 mg once daily-containing regimens discontinued TDF and switched to a non-NRTI or protease inhibitor. PBMC samples for TFV-DP were collected following discontinuation of TDF (N 8) over a period of 28 days postdose. While mean trough concentrations of TFV-DP from this study (76.4 [26.3] fmol/10^6 cells) were similar to those observed with historical data following administration of F/TDF 200/300 mg in HIV-infected participants in the Phase 3 Study GS-US-311-1089 (100.0 [139.0] fmol/10^6 cells), the variability was lower. This was accounted for in the simulations and is described further below.

#### **Analysis Method**

[figure not shown]
Observed TFV-DP concentration data from TAF or TDF was fit to a 1 compartment PK model with 1st order absorption and elimination, and no lag time, which was the 'best fit' based on comparison of Akaike information criterion (AIC) values with other models (ie., 2 compartment with or without lag time). The estimated slopes from the model were used to estimate half-life and simulate concentrations of TFV-DP over time following steady-state administration of either TAF 25 mg or TDF 300mg. Phoenix WinNonlin® 7.0. software was used for data fitting and simulations.

#### Results

#### **TFV-DP from TAF**

The median predicted half-life of TFV-DP ( $\sim$ 100 hours) following steady-state administration of TAF 25 mg was similar to the observed value ( $\sim$ 115 hours, N 26; Study GS-US-380-4017). Based on the median simulated TFV-DP concentration over time shown in Appendix Figure 1, participants ( $50^{th}$  percentile and above) are expected to have TFV-DP concentrations  $\geq$  40 fmol/ $10^6$  cells approximately 16 days after cessation of F/TAF 200/25 mg taken once daily.

Appendix Figure 1. Observed and Predicted PBMC-associated TFV-DP Concentrations with F/TAF 200/25 mg

[figure not shown]
**Green dots**: Observed PBMC associated TFV DP concentrations after the last dose of bictegravir/F/TAF 50/200/25 mg once daily for 28 days from Study GS US 380 4017

**Solid and dotted black lines:** Simulated median and 5th and 95th percentiles of TFV DP concentrations over time **Horizontal dotted black line:** Concentration of TFV DP expected to be associated with HIV prevention following administration of F/TDF 200/300 mg based on data from the iPrEX study (40 fmol/10^6 cells).

#### **TFV-DP from TDF**

The median predicted half-life of TFV-DP ( $\sim$ 106 hours) following steady-state administration of TDF 300 mg was similar to the observed value ( $\sim$ 132 hours, N 6; {Hawkins 2005}). Two subjects were excluded from the analysis as they had insufficient data to reliably estimate the TFV-DP half-life. To account for the lower variability observed in the Phase 1 dataset, observed variability from the Phase 3 study with F/TDF (GS-US-311-1089) was used to simulate concentration values for the 5th and 95th percentiles, resulting in a conservative estimate of TFV-DP concentrations for the 5th percentile. Based on the median simulated TFV-DP concentration over time shown in Appendix Figure 2, participants ( $50^{th}$  percentile and above) are expected to have TFV-DP concentrations  $\geq$  40 fmol/ $10^6$  cells approximately 10 days after cessation of F/TDF 200/300 mg taken once daily.

Appendix Figure 2. Observed and Predicted PBMC-associated TFV-DP Concentrations with F/TDF 200/300 mg

**Green dots**: Observed PBMC associated TFV DP concentrations after the last dose of a stable HIV ARV regimen containing TDF 300 mg once daily from {Hawkins 2005}.

**Solid and dotted black lines:** Simulated median and 5th and 95th percentiles of TFV DP concentrations **Horizontal dotted black line:** Concentration of TFV DP expected to be associated with HIV prevention following administration of F/TDF 200/300 mg based on data from the iPrEX study.

## **Summary**

These analyses demonstrate that PBMC-associated concentrations of TFV-DP are anticipated to be at or above the threshold associated with HIV prevention in participants (50th percentile and above) approximately 16 days and 10 days after cessation of multiple-dose F/TAF or F/TDF, respectively. As such, on-treatment HIV infections will be defined in GS-US-412-2055 as HIV infections diagnosed after first dose date through the last dose date +16 days for F/TAF or + 10 days for F/TDF.

## **Appendix 8.** Predicted HIV Incidence Rate from Rectal Gonorrhea Rates

The predicted HIV-1 incidence rate, in the absence of PrEP, will be estimated using data from a linear regression model characterizing the expected HIV incidence rate as a function of anal/rectal gonorrhea incidence rate (as an indicator of engaging in sexual risk behavior putting subject at risk of acquiring HIV). This model is constructed based on incidence rates for HIV and rectal gonorrhea in 8 studies with MSM not using PrEP {Mullick 2019}. The studies and rates considered for constructing the model are listed in Appendix Table 7.

Appendix Table 7. Incidence of Rectal Gonorrhea Infection and HIV Infection in HIV-uninfected MSM not using PrEP

[figure not shown]
Source Publication	Rectal Gonorrhea Incidence (per 100 PY)	HIV Incidence (per 100 PY)	Study Location
Morris SR, CID 2006 (EXPLORE)	3.5	2.5	United States
Jin F, JAIDS 2010	2.3	0.9	Australia
Sanders 2014*	9.3	35.2	Kenya
Molina JM, NEJM 2015 (IPERGAY)	15.5	6.6	France, Canada
Castillo R, JAIDS 2015	10.1	3.6	Peru
Kelley CF, AIDS 2015	6.2	3.8	United States
McGowan I, PLOS One 2016	16.1	6.4	United States
McCormack S, Lancet 2016 (PROUD)	33.1	9.0	United Kingdom
Girometti N, Sex Transm Infect 2017	33.0	8.3	United Kingdom

[figure not shown]
\* Sanders data excluded from the model {Mullick 2019}

Based on these data (excluding the Sanders 2014 rates) the constructed regression model is characterized by

$$\hat{v} = 1.8168 + 0.2218 \times x$$

where  $\hat{y}$  is the predicted HIV-1 incidence rate (events/100PY) in the absence of HIV prophylaxis and x is the rectal gonorrhea incidence rate (events/100PY).

To assess if treatment with F/TAF (or F/TDF) is superior to the historical placebo with respect to the HIV-1 incidence rate, the following steps will be done:

1) Construct a 2-sided 95% prediction band around the regression line for the predicted HIV-1 incidence rate in the absence of HIV prophylaxis given the observed rectal gonorrhea incidence rate for study participants receiving F/TAF. This 95% prediction interval is characterized below:

$$\hat{y} \pm t_{n/2} \times s_y \sqrt{1 + \frac{1}{n} + \frac{(x - \overline{x})^2}{(n - 1)s_x^2}}$$

where n is the total number of studies in the meta-analysis,  $s_y$  is the standard deviation of the regression model residuals,  $s_x$  is the standard deviation anal/rectal gonorrhea incidence rates,  $s_x$  is the average anal/rectal gonorrhea incidence rate, and  $t_{n,2}$  is the quantile for the 2-sided 95% t distribution with (t 2) degrees of freedom.

2) Construct a 2-sided 95% confidence interval for the observed HIV-1 incidence rate for study participants receiving F/TAF (or F/TDF). The 95% CI for the incidence rate is calculated using the following formula:

$$L_l = \frac{\chi_{2Y,\alpha/2}^2}{2D}$$

$$L_u = \frac{\chi_{2(Y+1),1-\alpha/2}^2}{2D}$$

where Y is the observed number of events,  $L_l$  and  $L_u$  are lower and upper confidence limits for Y respectively, D is the total follow-up duration, and  $\chi^2_{\nu,\alpha}$  is the chi-square quantile for upper tail probability on  $\nu$  degrees of freedom (Ulm, 1990).

3) If 
$$L_u = \min \left( L_u, \hat{y} - t_{n-2} \times s_y \sqrt{1 + \frac{1}{n} + \frac{(x - \overline{x})^2}{(n-1)s_x^2}} \right)$$
 then declare F/TAF (or F/TDF) superior to the historical placebo HIV-1 infection rate.

[figure not shown]

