## Appendix Table 5. HIV Infection Rates (Comparison to Predicted HIV Incidence Rate from Rectal Gonorrhea Rates), Full Analysis Sets

	Observed Rectal Gonorrhea Incidence Rate per 100 PY	Expected HIV Incidence Rate per 100 PY (95% Prediction Interval) Based on Observed Rectal Gonorrhea Rate	Observed F/TAF or F/TDF HIV Infection Rate per 100 PY (95% Exact CI)
F/TAF			
FAS, While At Risk of HIV Infection	X.XXX	x.xxx (x.xxx, x.xxx)	x.xxx (x.xxx, x.xxx)
Per Protocol, On-Treatment	x.xxx	x.xxx (x.xxx, x.xxx)	x.xxx (x.xxx, x.xxx)
F/TDF			
FAS, While At Risk of HIV Infection	x.xxx	x.xxx (x.xxx, x.xxx)	x.xxx (x.xxx, x.xxx)
Per Protocol, On-Treatment	x.xxx	x.xxx (x.xxx, x.xxx)	x.xxx (x.xxx, x.xxx)

Observed HIV infection rate and rectal gonorrhea incidence rate (number of events per 100 person years [PY], includes multiple events per subject, based on local laboratory tests) from GS US 412 2055. 95% exact CI from the single Poisson rate parameter (Ulm 1990).

Expected HIV incidence rate based on a regression model of rectal gonorrhea and HIV incidence rates in the absence of HIV prophylaxis (Mullick 2019).

Programming note: The HIV infection incidence rates will be computed on the populations and follow up timeframes specified in the primary efficacy analyses

(Section 6.1.1 6.2.3) as well as the PP on treatment sensitivity analysis (Section 6.2.6.) The rectal gonorrhea incidence rates will be computed based on laboratory data as specified in Section 9.2.1.1.

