**Appendix Table 8. Predicted HIV Incidencea Using Rectal Gonorrhea Incidence as the Determinant** 

Rectal Gonorrhea incidence (per 100 PY)	Predicted HIV Incidence Including 95% Prediction Interval (per 100 PY)
15	5.1 (2.51, 7.78)
20	6.3 (3.59, 8.91)
21	6.5 (3.80, 9.15)
22	6.7 (4.01, 9.38)
23	6.9 (4.21, 9.62)
24	7.1 (4.41, 9.86)
25	7.4 (4.62, 10.11)
30	8.5 (5.59, 11.34)
35	9.6 (6.63, 12.63)

a. Predictive model based on HIV and rectal gonorrhea regression analysis from 8 studies

Appendix Figure 4 below gives the power under different rectal gonorrhea rates and HIV infection rates. The power is calculated using the closed form power formula for the Poisson distribution, ie. not based on simulations.

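### SAP Appendix 8 misstates its historical-placebo rule in three places: one misprinted bound in Appendix Table 8, a loosely defined spread term, and a reversed chi-square convention

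*SAP*

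**What the plan says.** SAP Appendix 8 predicts the HIV rate without PrEP from the rectal gonorrhea rate. The model is "constructed based on incidence rates for HIV and rectal gonorrhea in 8 studies with MSM not using PrEP"; Appendix Table 7 lists nine sources and marks one as excluded. The fitted line is "1.8168 + 0.2218" times the gonorrhea rate.

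- **Step 1** builds a two-sided 95% prediction interval with a t quantile on n-2 degrees of freedom and a spread term s_y, which "is the standard deviation of the regression model residuals". It is evaluated "given the observed rectal gonorrhea incidence rate for study participants receiving F/TAF".
- **Step 2** builds an exact Poisson interval (L_l, L_u) for the observed HIV rate of F/TAF (or F/TDF). The quantile symbol "is the chi-square quantile for upper tail probability on" its degrees of freedom, and L_u carries the subscript 1-α/2.
- **Step 3** declares F/TAF (or F/TDF) superior to historical placebo by comparing L_u with the lower prediction bound.

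Appendix Table 8 gives the interval at nine gonorrhea rates. The row at 35 reads "9.6 (6.63, 12.63" (closing bracket omitted here). Appendix Table 5 has a column headed "Observed Rectal Gonorrhea Incidence Rate per 100 PY", with separate F/TAF and F/TDF blocks. Appendix 12 item 16(b) gives SAS code for the exact interval, using lower-tail chi-square quantiles.

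**The concern.** A prespecified decision rule should give the same answer whoever programs it. Here the wording, the worked table and the code do not agree. Appendix 12 contains no code for the prediction interval, so a programmer would work from the wording of s_y.

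The wording of s_y and of the chi-square quantile, taken literally, would both make superiority over historical placebo easier to declare. A smaller s_y raises the lower bound that the arm has to beat, and a reversed chi-square convention lowers the L_u that is compared with it. The misprint at 35 goes the same way if anyone reads the threshold from the table. The documents also leave open which gonorrhea rate sets the threshold for F/TDF.

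**Working it through.** **Inputs** (Appendix Table 7, excluded study omitted; gonorrhea rate, HIV rate, per 100 PY): (3.5, 2.5), (2.3, 0.9), (15.5, 6.6), (10.1, 3.6), (6.2, 3.8), (16.1, 6.4), (33.1, 9.0), (33.0, 8.3). From the SAP: 4250 PY per arm (Appendix Figure 4 note) and a planned HIV rate of 1.44 per 100 PY (Section 1.3.1).

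**Fit.** Least squares gives 1.8168 + 0.2218x, as printed. Mean x = 14.975, s_x = 12.236, SSE = 6.182, t on 6 df = 2.447.

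**Two readings of s_y**
- Residual standard error: sqrt(6.182/6) = 1.015.
- Ordinary SD of the residuals: sqrt(6.182/7) = 0.940.

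**Interval.** ŷ ± 2.447 × s_y × sqrt(1 + 1/8 + (x − 14.975)²/(7 × 12.236²)).

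| Gonorrhea rate | Printed | With 1.015 | Lower bound with 0.940 |
|---|---|---|---|
| 15 | 2.51, 7.78 | 2.51, 7.78 | 2.70 |
| 20 | 3.59, 8.91 | 3.59, 8.91 | 3.79 |
| 22 | 4.01, 9.38 | 4.01, 9.38 | 4.21 |
| 25 | 4.62, 10.11 | 4.62, 10.11 | 4.82 |
| 30 | 5.59, 11.34 | 5.59, 11.34 | 5.81 |
| 35 | **6.63**, 12.63 | **6.53**, 12.63 | 6.76 |

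Rows 21, 23 and 24 also reproduce with 1.015. In all, 17 of 18 bounds agree within about 0.005.

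**(a) Row 35.** ŷ = 9.578 and the half-width is 2.447 × 1.015 × 1.2278 = 3.050, so the interval is 6.53 to 12.63. The printed row is also off centre: its midpoint is (6.63 + 12.63)/2 = 9.63.

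**(b) Spread term.** With 0.940 the lower bounds rise by 0.19 (at 15) to 0.23 (at 35). The multiplier is effectively 2.447 × 0.940/1.015 = 2.265 on 6 df, which covers 93.6%. At a gonorrhea rate of 22 and 4250 PY, the largest HIV count that still passes goes from 144 to 152.

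**(c) Chi-square convention.** Take 20 events in 42.5 hundred PY, so 2(Y+1) = 42 df.
- Lower-tail quantile at 0.975: 61.78/(2 × 42.5) = 0.727 per 100 PY, the correct L_u.
- Literal reading, upper-tail probability 0.975: 26.00/85 = 0.306.

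At a gonorrhea rate of 22, the largest passing count would go from 144 to 195.

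**Effect at the planned rate.** 1.44 × 42.5 ≈ 61 events, L_u = 1.84 per 100 PY. The lowest bound in Table 8 is 2.51.

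**Which gonorrhea rate.** Step 1 names F/TAF only, step 3 decides for either arm, and Appendix Table 5 gives each arm its own rate. If each arm has its own threshold, chance separates the two. At 22 per 100 PY, the Poisson SE of one arm's rate is sqrt(22 × 42.5)/42.5 = 0.72. The lower bound rises by (4.212 − 3.799)/2 = 0.206 per unit of gonorrhea rate between 21 and 23. The SD of the difference in thresholds is 0.206 × 0.72 × sqrt(2) = 0.21 per 100 PY.

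**The case against.** The strongest reply is that nothing here is miscalculated where it counts. The phrase used for s_y is often shorthand for the residual standard error, no divisor is given, and it is paired with n-2 degrees of freedom. Table 8 shows that the authors used 1.015. This stands: a reader might infer that the printed thresholds rest on too small a spread, and the table refutes that. What remains is that the definition should name the quantity.

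On row 35, step 3 evaluates the formula at the observed rate, and no text makes Table 8 a lookup. This also stands, so the misprint alters a decision only if the table is read off directly. On the chi-square wording, Appendix 12 item 16(b) applies to every exact 95% interval and is correct, so the implemented limits should be right. Some symbols in Appendix 8 are garbled in the available text, and I put no weight on those. The tail wording itself is legible and conflicts with the code.

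A reader might also infer that a threshold for each arm is an error, since randomised arms share one expected background risk. The documents do not support that. Comparing an arm with a prediction from its own exposure marker is coherent, and the between-arm question is answered by the Poisson rate ratio in Section 6.2.5, not by comparing two verdicts. The chance SD of 0.21 is also small beside the prediction half-width of 2.69 at a rate of 22.

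**Conclusion.** The point holds as three misstatements and one unreconciled choice of input. The lower bound at 35 is 0.10 too high. The wording of s_y, if coded with divisor n-1, would raise the threshold by about 0.2 per 100 PY. The chi-square wording contradicts the SAP's own code and, if followed, would more than halve L_u in the 20-event example (0.306 against 0.727).

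The practical stake is low. Apart from row 35, the printed thresholds are not too lenient. At the planned HIV rate the upper limit of 1.84 is below every tabulated bound under either spread term, and a verdict could change only for an arm close to its threshold.

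This rests on the eight pairs in Appendix Table 7 and on 4250 PY per arm. The SAP ties that figure to the primary analysis; with the longer follow-up at the end of the blinded phase, the chance difference between arm thresholds would be smaller. It would be larger if repeat gonorrhea infections, which Appendix Table 5 counts, cluster within participants. Section 6.2.8, where exploratory efficacy analyses would be described, has no text in the public copy, so the standing of this comparison cannot be judged further.

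**What to change.** 1. Correct the Appendix Table 8 row at 35 to 9.6 (6.53, 12.63).
2. Define s_y as the residual standard error, sqrt(SSE/(n-2)), which is 1.015 for these studies.
3. Describe the chi-square quantile by lower-tail probability, in line with Appendix 12 item 16(b).
4. State in step 1 which gonorrhea rate sets the threshold for each arm, so that it agrees with Appendix Table 5.

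An option, not a correction: in the FAS rows of Appendix Table 5, use one threshold from the gonorrhea rate pooled over both randomised arms, and still show the arm-specific rates. This removes the chance difference between thresholds. It should not extend automatically to the Per Protocol on-treatment rows, where post-randomisation selection and the 16-day and 10-day windows break the randomised balance.

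The cost is one table cell and three sentences, plus one pooled rate in the program if the option is taken. No new data are needed, and thresholds already computed with 1.015 do not move.
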